Lirilumab will be administered as a 240 mg IV infusion over 60 minutes (\pm 5 minutes) on Day 1 of Cycle 1 and then Day 1 of every other cycle thereafter (ie, Cycle 3, Cycle 5, etc). Lirilumab will be administered after nivolumab on visit days when both agents are given. Intrasubject dose escalation of lirilumab is not allowed.

Treatment Cycles and Duration of Treatment:

Study treatment will be administered in continuous 14-day cycles. Subjects will continue to receive study treatment for up to 2 years as long as the subject is deriving benefit and has not met any of the Protocol-defined conditions for treatment discontinuation. Intrasubject dose-escalation is not permitted.

Study Schedule/Procedures:

The study comprises the following parts:

- **Screening:** Up to 28 days before enrollment. Screening will begin at the time that the subject signs the informed consent and will continue until the date the subject is enrolled in the study (Cycle 1 Day 1).
- **Treatment:** Treatment cycles will be 14 days in length. Subjects will have regularly scheduled study visits on Day 1 (± 3 days) of each cycle. Clinic visits will also occur on Day 8 (± 1 day) during the first 3 cycles.
- **End of treatment:** + 7 days after withdrawal from study treatment.
- **Safety follow-up:** 30 days (+ 7 days), 100 days (± 7 days), and 150 days (± 7 days; Treatment Group B only) after the last dose of study treatment.

Safety Assessments:

Subjects will have regularly scheduled study visits at the clinical site on Day 1 of every cycle where targeted physical examinations, vital sign collection, collection of concomitant medications, and AE assessments will be performed. Twelve-lead ECGs will be performed at screening, Cycle 1 Day 1, Cycle 2 Day 1, and at the end-of-treatment visit. Laboratory assessments will be collected during each treatment cycle. Toxicities will be monitored continuously and will be graded using the National Cancer Institute's CTCAE v4.03 criteria.

Regular telephone conferences with study investigators will be scheduled by the sponsor in order to review cohort-specific data and overall safety data, agree on dose escalation, adjudicate individual high-grade AEs as potentially dose-limiting, and guide other major study decisions.

Efficacy Assessments:

Disease assessments will be performed based on RECIST v1.1 [REDACTED]

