Administer ipilimumab		X		X					Ipilimumab will be administered on Cycle 1 Day 1 and then on Day 1 of every 3rd cycle (Cycles 4, 7, 10, etc).
Efficacy Assessments									
Radiologic tumor assessments	X				X				The same imaging technique should be used in a subject throughout the study. If imaging shows PD, an imaging assessment should be performed at a minimum of 4 weeks and maximum of 8 weeks later to confirm PD █ See Section 7.6 for complete details on imaging requirements.

^a On-study imaging will be performed at 8 and 16 weeks (± 7 days) after the start of treatment and then every 12 weeks (± 7 days) thereafter until the end of study treatment. Imaging should follow calendar days starting with Day 1 of study treatment and should NOT be adjusted for delays in cycle starts.

^b The mandatory safety follow-up visits should be conducted approximately 30 and 100 days after the last dose of study treatment or before the initiation of a new anticancer treatment, whichever comes first.

^c Only required for Day 8 visits if there are ongoing AEs > Grade 2.

Table 22: Schedule of Laboratory Assessments – Treatment Group A (Epacadostat + Nivolumab + Ipilimumab)

Visit	Screening	Treatment Period (14-Day Cycles)			EOT	Follow-Up	Comments
		Cycles 1 Through 3		Cycle 4 and Beyond		30 Days After EOT	
		Day 1	Day 8	Day 1			
Evaluation/Window	Days -28 to -1	± 3 Days	± 1 Day	± 3 Days	+ 7 Days	+ 7 Days	
Local Laboratory Tests^a							
Serum chemistry	X	X	X	X	X	X	Additional assessment of serum chemistry as clinically indicated.
Hematology with differential	X	X		X	X	X	Additional assessment of hematology as clinically indicated.
Liver chemistry tests	X	X	X	X	X	X	If baseline liver chemistry tests are WNL and increase to ≥ Grade 1, testing should be performed twice weekly until resolved to baseline. If baseline liver chemistry tests were Grade 1 at baseline and increase to ≥ Grade 2, twice weekly testing should be performed until resolved to ≤ Grade 1.
Coagulation panel	X			X	X		Screening, Cycle 4, and every 3rd cycle thereafter.
Endocrine function tests	X			X	X	X	Screening, Cycle 4, and every 3rd cycle thereafter.
Urinalysis	X				X		
Hepatitis B and C	X						
Serum pregnancy test ^b (childbearing females only)	X				X		Required for all women of childbearing potential during screening; must be within 72 hours before the first dose of study treatment.

^a All safety laboratory assessments will be performed locally.

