6.4. Follow-Up

6.4.1. Safety Follow-Up

The safety follow-up period is the interval between the EOT visit and the scheduled follow-up visits, which should occur approximately 30 days (+ 7 days), 100 days (\pm 7 days), and 150 days

(± 7 days; Treatment Group B only) after the EOT visit (or after the last dose of study treatment if the EOT visit was not performed). Adverse events and SAEs must be reported up until at least 100 days after the last dose of study treatment for Treatment Group A, up until at least 150 days after the last dose of study treatment for Treatment Group B, or until toxicities resolve, return to baseline, or are deemed irreversible, whichever is longer. Reasonable efforts should be made to have the subject return for the follow-up visits and to report any AEs that may occur during this period. If a subject is scheduled to begin a new anticancer therapy before the end of the safety follow-up period, the applicable safety follow-up visit should be performed before new anticancer therapy is started. After the safety follow-up period, there will be no additional assessments and the study will be considered complete.

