6.5. End of Study

Subjects will be considered as having completed the study if they meet any of the following criteria:

- Subject dies, and a date of death is available.
- Subject is known to have died; however, the date of death cannot be obtained.
Note: Every effort must be made to obtain the date of death.
- Consent is withdrawn for any further contact related to this study.
 - Subjects may choose to withdraw from the study at any time without penalty of jeopardizing their health care or loss of benefits to which they are otherwise entitled. Every reasonable effort should be made to determine the reason a subject withdraws prematurely, and this information should be recorded in the eCRF.
- The study is terminated by the sponsor.
- The study is terminated by the local health authority, IRB, or IEC.
- The subject completes the safety follow-up period.

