8.1.2. Reporting

Adverse events that begin or worsen after informed consent should be recorded on the Adverse Events form of the eCRF. Conditions that were already present at the time of informed consent should be recorded on the Medical History form in the eCRF. Monitoring for the occurrence of new AEs should be continued for at least 100 days after the last dose of study treatment for Treatment Group A, and 150 after the last dose of study treatment for Treatment Group B. Adverse events (including laboratory abnormalities that constitute AEs) should be described using a diagnosis whenever possible rather than by individual underlying signs and symptoms.

The term "disease progression" should be recorded as an AE/SAE only if there are no other identifiable AEs/SAEs associated with the disease progression at the time of reporting. For events associated with disease progression, the relevant signs and symptoms should be reported using a diagnosis whenever possible rather than individual underlying signs and symptoms. When a clear diagnosis cannot be identified, each sign or symptom should be reported as a separate AE. If the events resulting from disease progression meet the criteria for an SAE (eg, resulted in hospitalization, a life-threatening event, or death), the specific event(s) should be reported as an SAE(s) as described in Section 8.3.2. In both cases (ie, AEs or SAEs related to disease progression), it should be indicated that each event (reported as a diagnosis or as signs and symptoms) is related to disease progression on the Adverse Events form of the eCRF.

The severity of AEs will be assessed using CTCAE v4.03 Grades 1 through 5. If an event is not classified by CTCAE, the severity of the AE will be graded according to the scale below to estimate the grade of severity:

Grade 1	Mild; asymptomatic or mild symptoms; clinical or diagnostic observations only; intervention not indicated.
Grade 2	Moderate; minimal, local, or noninvasive intervention indicated; limiting age-appropriate activities of daily living.
Grade 3	Severe or medically significant but not immediately life-threatening; hospitalization or prolongation of hospitalization indicated; disabling; limiting self-care activities of daily living.
Grade 4	Life-threatening consequences; urgent intervention indicated.
Grade 5	Death due to AE

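### In Treatment Group A the final safety visit may fall up to 7 days before the 100-day adverse-event minimum, with no scheduled contact afterwards

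*Combined protocol and SAP*

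**What the plan says.** - **Visit windows.** The synopsis (Study Schedule/Procedures) places the safety visits at "30 days (+ 7 days), 100 days (± 7 days), and 150 days" after the last dose; the 150-day visit applies to Treatment Group B only. Section 6.4.1 and the window row of Table 21 give the same windows for the 30- and 100-day visits. The 30-day window is one-sided and the 100-day window is two-sided.
- **Starting point.** The synopsis counts from the last dose, and so does the footnote to Table 21: "The mandatory safety follow-up visits should be conducted approximately 30 and 100 days after the last dose of study treatment". Section 6.4.1 counts "after the EOT visit (or after the last dose of study treatment if the EOT visit was not performed"), and the column heads of Table 21 also count from EOT. By the synopsis, the EOT visit may itself take place up to "7 days after withdrawal from study treatment".
- **End of follow-up.** Section 6.4.1 defines the safety follow-up period as running to the scheduled visits, and adds: "After the safety follow-up period, there will be no additional assessments and the study will be considered complete". Section 6.5 lists among the criteria for completing the study: "The subject completes the safety follow-up period".
- **Required collection.** Section 6.4.1: "Adverse events and SAEs must be reported up until at least 100 days after the last dose of study treatment for Treatment Group A", or until toxicities resolve if that is longer. Section 8.1.2: "Monitoring for the occurrence of new AEs should be continued for at least 100 days after the last dose of study treatment".
- **SAE reporting.** Section 8.3.2 ends routine SAE reporting at the earliest of the last study visit, 100 days after the last dose, or new anticancer therapy. For Group A, SAEs more than 100 days after the last dose are reported only if the investigator suspects a causal link.
- **Who is affected.** The synopsis and Section 4.1 state that no one enrolled in Group B.

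**The concern.** For every enrolled subject the 100-day visit is the last planned contact. Because its window opens a week early, a site can follow the schedule exactly, complete the subject's study, and still have asked about adverse events for less than the stated minimum. The 30-day visit shows that the protocol already has a form of window that avoids this.

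At stake is a small part of the late safety record. Safety is the primary Phase 1 endpoint, and by the note in Section 9.4 efficacy tables are replaced by listings while summary tables are kept only for selected safety analyses. Section 1.6 notes that some immune-related events, such as raised liver enzymes and endocrinopathies, appear later than others. The passages also disagree on the starting point of the visit and on the end of SAE reporting, so two sites could close follow-up at different times and both be compliant.

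**Working it through.** The plan states no figure to reproduce; the check is day arithmetic on its own windows. Days are counted from the last dose.

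**1. Visit counted from the last dose** (synopsis; Table 21 footnote).
Earliest visit = 100 − 7 = Day 93; latest = 100 + 7 = Day 107.
Gap = 100 − 93 = 7 days, or 7/100 = 7% of the required period.

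**2. Visit counted from the EOT visit** (Section 6.4.1; Table 21 column heads).
Let L be the days from the last dose to the EOT visit. Earliest visit = L + 100 − 7 = L + 93.
Gap = max(0, 100 − (L + 93)) = max(0, 7 − L).

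| L (days) | Earliest visit | Gap (days) |
|---|---|---|
| 0 | Day 93 | 7 |
| 3 | Day 96 | 4 |
| 7 | Day 100 | 0 |
| 14 | Day 107 | 0 |

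If withdrawal falls on the day of the last dose, the EOT window gives L from 0 to 7. If withdrawal follows a dosing delay (Section 5.4.4 allows up to 28 days), L can be longer and the gap is 0. Over both anchors the gap at the earliest compliant visit is 0 to 7 days.

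**3. Does anything else cover those days?** Table 21 has no later contact, and Section 6.4.1 rules out further assessments. Its extension for toxicities, and the similar one in Section 5.5.2, keep events that are already present under follow-up. Neither schedules a contact that would detect a new one.

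**4. SAE reporting.** Under Section 8.3.2, with no new anticancer therapy, the end of routine reporting is the earlier of the last visit and Day 100. With a Day 93 visit, that is Day 93. Section 6.4.1 gives at least Day 100 for the same events. The suspected-causality rule in Section 8.3.2 begins only after Day 100, so an SAE starting on Days 94 to 100 falls under neither of that section's rules.

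**5. With a one-sided window.** Counted from the last dose, 100 days (+ 7 days) gives Day 100 to Day 107 and a gap of 0. Counted from EOT, the earliest visit is L + 100, so the gap is also 0.

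**6. Group B.** Only the 150-day visit is final there. Earliest = 150 − 7 = Day 143, a gap of up to 7 days (7/150 = 4.7%). With no subjects enrolled this is theoretical.

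**The case against.** The strongest reply is that the duty to collect does not depend on the visit. Sections 6.4.1 and 8.1.2 each set a 100-day minimum in their own right, so a site that sees a subject on Day 93 still owes reporting to Day 100 and can meet it by telephone or through a spontaneous report. The Table 21 footnote and Section 6.4.1 call the visit days approximate, and an explicit minimum can be read as prevailing over them. This stands. A reader might infer that the 100-day minimum cannot be met, or that the days are wholly unobserved; the documents support only that no scheduled contact covers them.

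A reader might also infer that about half of subjects are affected, because 7 of the 15 permitted days fall before Day 100. That needs visits spread evenly over the window and counted from the last dose. If they are counted from EOT instead, with EOT also spread evenly over 0 to 7 days, 28 of 8 × 15 = 120 combinations (23%) fall early. The documents support neither spread, so no share should be quoted.

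Nor does the point reach the dose decisions. By Section 5.4.2 the DLT period ends on Day 42 of treatment. No planned adverse-event analysis uses a fixed 100-day window, and the definition of a treatment-emergent event in Section 9.4.2.1 has no end date. Follow-up already varies far more by design, with treatment of up to 2 years and visits brought forward when new anticancer therapy starts.

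What the reply does not remove is the mismatch between window and minimum, the two anchors, and the SAE cut-off in Section 8.3.2, which on its wording does release the site at an early last visit.

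**Conclusion.** The inconsistency is real and small. In Group A a compliant final visit can leave 0 to 7 days of the required 100 without a scheduled contact, depending on the anchor and on where in the window the visit falls. Section 8.3.2 would end routine SAE reporting at that visit. The exposure is limited to events that begin in those days; existing toxicities are followed under other provisions, and DLT and MTD decisions are untouched. The upper figure of 7 days assumes a visit at the early edge, counted from the last dose or from an EOT visit on the day of the last dose. The expected number of missed events cannot be calculated from the documents, but is likely to be low. It is worth correcting because the correction is cheap and this schedule governs every enrolled subject. A reader might extend the point to Group B's 100-day visit, but that visit is not final, so the argument does not apply to it.

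**What to change.** 1. In the synopsis, Section 6.4.1 and Table 21, set the Group A final visit at 100 days (+ 7 days), the one-sided form that the 30-day visit already has.
2. Count it from the last dose everywhere: the synopsis and the Table 21 footnote already do; Section 6.4.1 and the Table 21 column heads need to change.
3. Align the end of SAE reporting in Section 8.3.2 with the minimum of at least 100 days in Section 6.4.1, and state in both places whether new anticancer therapy ends collection.

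If the two-sided window is kept, a required contact on or after Day 100 for anyone seen earlier would also close the gap, provided step 3 is made. Group B's 100-day visit needs no change; its 150-day window could be edited for consistency, with no practical effect.

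The cost is a text edit in a few places. Some final visits fall up to a week later, and sites have 8 permitted days (100 to 107) instead of 15 (93 to 107). No visit or procedure is added. Visits brought forward because new anticancer therapy is starting are a separate exception that the window edit does not affect.

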Table 30:	Sample Size Calculation for Each Phase 2 Cohort: Comparing to a Known Proportion	98
Table 31:	Criteria for Clinically Notable Vital Sign Abnormalities.....	100
Table 32:	Criteria for Clinically Notable Electrocardiogram Abnormalities	101

LIST OF FIGURES

Figure 1:	Study Design.....	46
-----------	-------------------	----

LIST OF ABBREVIATIONS

The following abbreviations and special terms are used in this clinical study Protocol.

Abbreviation	Definition
█	█
AE	adverse event
ALK	anaplastic lymphoma kinase gene
ALT	alanine aminotransferase
ANC	absolute neutrophil count
aPTT	activated partial thromboplastin time
AST	aspartate aminotransferase
BCG	Bacillus Calmette-Guérin
BID	twice daily
BRAF	BRAF gene
BMS	Bristol-Myers Squibb
CA	cancer antigen
CFR	Code of Federal Regulations
CI	confidence interval
CL	clearance
CNS	central nervous system
CR	complete response
CrCl	creatinine clearance
CT	computed tomography
CTCAE	Common Terminology Criteria for Adverse Events
ctDNA	circulating tumor DNA
CTLA-4	cytotoxic T-lymphocyte-associated protein 4
DC	dendritic cell
DLT	dose-limiting toxicity
DOR	duration of response
eDMC	external Data Monitoring Committee
EOT	end of treatment
ECG	electrocardiogram
ECOG	Eastern Cooperative Oncology Group
eCRF	electronic case report form
EGFR	epidermal growth factor receptor gene
EU	European Union
FDA	Food and Drug Administration

Abbreviation	Definition
FFPE	formalin-fixed paraffin-embedded
GCP	Good Clinical Practice
GFR	glomerular filtration rate
GI	gastrointestinal
HBsAg	hepatitis B surface antigen
HBV	hepatitis B virus
HCV	hepatitis C virus
HIPAA	Health Insurance Portability and Accountability Act of 1996
HIV	human immunodeficiency virus
HLA	human leukocyte antigen
HPV	human papillomavirus
ICF	informed consent form
ICH	International Conference on Harmonisation
████	██
████	██
IDO1	indoleamine 2,3-dioxygenase 1
IEC	independent ethics committee
IgG	immunoglobulin G
IN	Investigator Notification
INR	international normalized ratio
████	██
irAE	immune-related adverse event
IRB	institutional review board
████	██
IRT	Interactive Response Technology
████	██
IV	intravenous
JTc	corrected JT interval
KIR	killer cell immunoglobulin-like receptor
MAOI	monamine oxidase inhibitor
MedDRA	Medical Dictionary for Regulatory Activities
MEL	melanoma
MRI	magnetic resonance imaging
MTD	maximum tolerated dose
NK	natural killer
nM	nanomolar

Abbreviation	Definition
NSCLC	non–small cell lung cancer
ORR	objective response rate
█	█
PAD	pharmacologically active dose
PD	progressive disease
PD-1	programmed cell death protein 1
PDAC	pancreatic ductal adenocarcinoma
PD-L1	programmed cell death ligand 1
PD-L2	programmed cell death ligand 2
PET	positron emission tomography
PET/CT	positron emission tomography - computed tomography
PFS	progression-free survival
█	█
PR	partial response
PT	prothrombin time
Q2W	once every 2 weeks
Q3W	once every 3 weeks
Q4W	once every 4 weeks
Q6W	once every 6 weeks
QTc	corrected QT interval
RCC	renal cell carcinoma
RECIST v1.1	Response Evaluation Criteria In Solid Tumors version 1.1
ROS1	ROS1 gene
RP2D	recommended Phase 2 dose
SAE	serious adverse event
SCCHN	squamous cell carcinoma of the head and neck
SD	stable disease
SMC	Safety Monitoring Committee
SmPC	summary of product characteristics
SNRI	serotonin norepinephrine reuptake inhibitor
SS	serotonin syndrome
SSRI	selective serotonin reuptake inhibitor
SUSAR	suspected unexpected serious adverse reaction
Treg	T regulatory cell
ULN	upper limit of normal
US	United States of America

1. INTRODUCTION

1.1. Background

1.1.1. The Role of the Immune System in Cancer and Overall Study Rationale

The immune response is controlled by a series of checks and balances to allow for robust immune responses to pathogens while preventing either an excessive inflammatory event or an autoimmune response. Through immune surveillance, the immune system has also been shown to recognize, attack, and destroy tumor cells ([Wolchok and Saenger 2008](#)). Targeting the immune system as an anticancer strategy is a proven and effective approach for the treatment of many types of cancer, and immunotherapy is now an accepted standard of care in several tumor types. Approved checkpoint inhibitors, including the PD-1–blocking antibody nivolumab and the CTLA-4 blocking antibody ipilimumab, allow for the immune response to continue to proliferate in spite of inhibitory signals. Both of these agents have demonstrated antitumor activity when administered as monotherapy, and emerging data suggest that combined blockade of both targets results in an enhanced antitumor response ([Larkin et al 2015](#), [Hellmann et al 2016](#), [Goldman et al 2017](#)); however, despite the encouraging activity observed with dual PD-1 and CTLA-4 blockade, multiple other immune inhibitory mechanisms are present concurrently within the tumor microenvironment, suggesting that combination approaches targeting additional mechanisms of immune tolerance may be required for optimal therapeutic effect ([Quezada and Peggs 2013](#)). Two promising approaches to overcoming these mechanisms include inhibition of IDO1 and blockade of KIR inhibitory receptors.

1.1.2. Inhibition of Indoleamine 2,3-Dioxygenase 1 as a Target for Cancer

IDO1 is a heme-containing, monomeric oxidoreductase that catalyzes the degradation of the essential amino acid tryptophan to N-formyl-kynurenine. Kynurenine can be subsequently metabolized through a series of enzymatic steps to nicotinamide adenine dinucleotide. IDO1 is the first rate-limiting enzyme in one of the catabolic pathways of tryptophan.

The expression and activity profiles of IDO1 are distinct from those of tryptophan dioxygenase, an enzyme predominantly expressed in liver that catalyzes the same enzymatic reaction as IDO1 and maintains proper tryptophan balance in response to dietary uptake. In contrast to tryptophan dioxygenase, IDO1 is expressed in a variety of tissues, with particularly high levels found in areas of contact with potential sources of immune challenge (eg, gut, respiratory tract, placenta, spleen), consistent with a role for regulating tryptophan metabolism in a local microenvironment ([Mellor and Munn 2004](#)). Within the immune system, IDO1 activity is specifically induced in cells such as DCs and macrophages at localized sites of inflammation ([Munn and Mellor 2007](#)).

IDO1-driven oxidation of tryptophan results in a strong inhibitory effect on the development of T-cell–mediated responses by blocking T-cell activation and inducing T-cell apoptosis ([Mellor et al 2003](#)). Both the reduction in local tryptophan levels and the production of tryptophan catabolites that are inhibitory to cell proliferation contribute to the immunosuppressive effects ([Frumento et al 2002](#)) such as DC maturation and T-cell growth arrest and cell death ([Mellor and Munn 1999](#)). IDO1 activity also promotes the differentiation of naive T cells to cells with a regulatory phenotype (Treg; [Fallarino et al 2006](#)). Because increased

Treg activity has been shown to promote tumor growth, and Treg depletion has been shown to allow an otherwise ineffectual antitumor immune response to occur (Zou 2006), IDO1-driven expansion of Tregs may provide an additional mechanism whereby IDO1 could promote an immunosuppressive environment.

A critical role for IDO1 in immunomodulation has been confirmed in numerous animal models, including models of allograft tolerance, inflammation, and cancer (Mellor and Munn 2004). While IDO1 inhibition can exacerbate disease in models of autoimmune disorders (Mellor and Munn 2004), IDO1 null mice show no evidence of susceptibility to developing spontaneous autoimmunity or alterations in immune system development (Mellor et al 2003), suggesting that IDO1 inhibition, in a therapeutic setting, may produce minimal side effects in subjects without pre-existing autoimmune conditions.

Within the context of cancer, there are several lines of evidence to suggest that IDO1 is a key regulator of the immunosuppressive mechanisms responsible for tumor escape from immune surveillance. Several groups have demonstrated that blockade of IDO1 activity can directly influence the ability of tumor-bearing animals to reject tumors (Uyttenhove et al 2003, Muller et al 2005). In addition, studies with 1-methyl-tryptophan demonstrate that IDO1 inhibition dramatically increases the efficacy of various chemotherapeutic agents (eg, platinum compounds, taxane derivatives, cyclophosphamide) without increased toxicity (Muller et al 2005). Although the specific mechanisms responsible for this potentiation remain to be fully elucidated, the effects were not observed in T-cell-deficient animals, suggesting that the results may be the consequence of the disablement of immunosuppressive mechanisms that exist within the tumor microenvironment.

Based on studies examining serum levels of tryptophan and kynurenine, IDO1 appears to be chronically activated in subjects with cancer, and IDO1 activation correlates with more extensive disease (Huang et al 2010, Weinlich et al 2007). IDO1 has subsequently been found to be overexpressed by a wide variety of human tumor cell types, as well as by the DCs that localize to the tumor-draining lymph nodes (Uyttenhove et al 2003, Munn et al 2004). Increased expression of IDO1 in tumor cells has been shown to be an independent prognostic variable for reduced OS in subjects with MEL, head and neck, ovarian, colorectal, and pancreatic cancers (Okamoto et al 2005, Laimer et al 2011, Brandacher et al 2006, Ino et al 2006, Nakamura et al 2007, Witkiewicz et al 2008, Hamid et al 2009).

Together, these results suggest that the IDO1 pathway is a key regulatory element responsible for the induction and maintenance of tumor immune tolerance. Small molecule inhibitors of IDO1 may provide an innovative and tractable method to treat malignancies.

